1.3 Research Questions of the Study

Q1: How do 4-week interventions of traditional Yo-Yo training, ball-dribble integrated Yo-Yo training, and small-sided games (SSGs) influence aerobic capacity in adolescent soccer players?

Q2: How do 4-week interventions of traditional Yo-Yo training, ball-dribble integrated Yo-Yo training, and small-sided games (SSGs) influence anaerobic performance in adolescent soccer players?

Q3: Are there between-group differences in the improvements across aerobic, capacities?

Q4: Are there between-group differences in the improvements across anaerobic capacities?

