3.1 Participants

Participants should be recruited from middle school soccer teams. Participants shall fulfill all the following inclusion criteria to be included in the study: (1) be aged between 13 and 18 years; (2) have received at least one year of formal football training; (3) have no history of major sports-related injuries; (4) be in good general health, without smoking or alcohol consumption habits; and (5) have no known psychological or psychiatric disorders that may affect participation; (6) have not participated in any similar intervention within the past year; (7) attend the training sessions regularly. Participants should be excluded according to the following criteria: 1. are outside the age range of 13–18 years; 2. have less than one year of formal football training experience; 3. have a history of major sports-related injuries; 4. have chronic diseases or unhealthy habits such as smoking or alcohol consumption; 5. have known psychological or psychiatric disorders that may affect participation; 6. have participated in similar training interventions within the past year; 7. fail to attend at least 75% of the 12 training sessions.

The required sample size was calculated using G*Power 3.1 software based on a repeated-measures ANOVA (within-between interaction). The average effect size (f) was set at 0.25 (Cherni et al., 2025; Li et al., 2022), with a significance level of 0.05, and the desired statistical power of 0.80 achieved. The calculations indicated that a minimum of 42 participants are required in total, considering the 20% dropout, at least 50 participants should be recruited at the screening session.

The experimental procedures will be explained to participants and their parents at the screening-baseline. Before data collection, the written informed consent should also be provided. During the study, the participants will all attend regular schools and

football trainings. This research should receive approval from the Ethics Committee of University of Macau.

[figure not shown]

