3.5 Statistical Analysis

Data analysis will be conducted using SPSS 29.0. First, descriptive statistics will be performed to summarize sample characteristics. Independent samples t-tests will be used to compare baseline differences between groups. The Shapiro-Wilk test will be applied to assess normality; if data violate normality assumptions, appropriate adjustments will be implemented.

A two-way repeated measures ANOVA (group \times time) will be utilized to examine between-group effects, time effects, and interaction effects on outcomes including aerobic and anaerobic performance. If significant interactions are detected, Bonferroni post-hoc tests will be conducted to identify simple main effects.

Effect sizes will be reported as partial eta-squared (η^2) for ANOVA results, with $\eta^2 < 0.06$ considered small, 0.06-0.14 moderate, and >0.14 large. Within-group effect sizes will be calculated using Cohen's d, where $d = 0.2$, 0.5 , and 0.8 represent small, medium, and large effects, respectively. Statistical significance is set at $\alpha = 0.05$, and results will be presented as mean \pm standard deviation (Mean \pm SD).

References

- Akdoğan, E., Yılmaz, İ., Köklü, Y., Alemdaroğlu, U., & Cerrah, A. O. (2021). The effect of isolated or combined small-sided games and speed endurance training on physical performance parameters in young soccer players. *Kinesiology*, 53(1), 78–85. <https://doi.org/10.26582/k.53.1.10>
- Badenhorst, J. (2017). *The effect of the growth spurt on strength, power, speed and agility training in boys during mid-adolescence* [PhD Thesis, North-West University (South Africa), Potchefstroom Campus]. <https://repository.nwu.ac.za/handle/10394/30657>
- Clemente, F. M., Praça, G. M., Aquino, R., Castillo, D., Raya-González, J., Rico-González, M., Afonso, J., Sarmiento, H., Silva, A. F., Silva, R., & Ramirez-Campillo, R. (2023). Effects of pitch size on soccer players' physiological, physical, technical, and tactical responses during small-sided games: A meta-analytical comparison. *Biology of Sport*, 40(1), 111–147. <https://doi.org/10.5114/biolsport.2023.110748>

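### No pairwise between-arm difference in improvement, with a confidence interval, is planned, and the arm-by-arm Cohen's d labels cannot take its place

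*Combined protocol and SAP*

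**What the plan says.** Section 3.5 of the combined protocol and SAP assigns the comparison of programmes to a group-by-time repeated-measures ANOVA, which "will be utilized to examine between-group effects, time effects, and interaction effects on outcomes including aerobic and anaerobic performance". Follow-up is conditional: "If significant interactions are detected, Bonferroni post-hoc tests will be conducted to identify simple main effects".

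Two kinds of effect size are planned. For the ANOVA, "Effect sizes will be reported as partial eta-squared", with bands cut at 0.06 and 0.14. For change within an arm, "Within-group effect sizes will be calculated using" Cohen's d, where 0.2, 0.5 and 0.8 "represent small, medium, and large effects, respectively". The SD that goes into d is not named. Results are to be shown as mean ± SD, and no confidence interval is mentioned.

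Section 1.3 asks in its fourth question: "Are there between-group differences in the improvements across anaerobic capacities". The third question asks the same for aerobic capacity. In Section 1.4, H3 and H4 are pairwise: each says that two named programmes are equivalent and that both beat the third. H1 and H2 ask only whether players improve.

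**The concern.** Partial eta-squared for a three-arm interaction is a between-arm effect size, but an overall one. It does not say which programme gained more, over which other, or by how much. The post-hoc tests run only after a significant interaction. They are aimed at simple main effects, which may themselves be time effects within each arm. If the interaction is not significant, the plan yields no pairwise comparison at all.

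The only planned effect size that gives the direction and size of change programme by programme is therefore the labelled within-arm d. A report built on this plan could show three labels and no estimate of the differences that H3 and H4 concern. Three labels side by side carry no measure of sampling error. With an unnamed SD, the label can also depend on a choice made after the data are seen.

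**Working it through.** **Number per arm.** Section 3.1 gives f = 0.25, "with a significance level of 0.05, and the desired statistical power of 0.80 achieved", a within-between interaction and a minimum total of 42. With k = 3 arms, m = 2 time points and an assumed pre-post correlation of 0.5 (none is stated):

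- noncentrality = f² × N × m / (1 − r) = 0.0625 × 42 × 2 / 0.5 = 10.5
- degrees of freedom = 2 and 39, giving power 0.803

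The stated 42 is reproduced, so there are 42 / 3 = 14 players per arm. Section 3.2 also mentions four groups. Three are used here because only three are defined.

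**Do equal true gains get equal labels?** In 40,000 simulated trials per setting, pre and post values were bivariate normal, with 14 per arm and the same true gain in all three arms. d is the mean change divided by the average of the arm's pre and post SDs. Cuts at 0.2, 0.5 and 0.8 give four bands, counting below small as one. The true d and the correlation r are assumptions. The table shows the share of trials in which the three arms do not all fall in one band.

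| True d | r = 0.5 | r = 0.8 | r = 0.9 |
|---|---|---|---|
| 0 | 54% | 33% | 16% |
| 0.2 | 83% | 79% | 77% |
| 0.35 | 90% | 79% | 63% |
| 0.5 | 91% | 84% | 80% |
| 0.65 | 89% | 83% | 75% |
| 0.8 | 82% | 78% | 76% |
| 1.0 | 55% | 42% | 34% |
| 1.2 | 23% | 9% | 5% |

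At d = 1.5 the share is 2% or less. Standardising by the pre-test SD gives similar figures. Standardising by the SD of change gives figures close to the r = 0.5 column. With 16 per arm, the range for d of 0.2-0.8 is 58-90%. The cause is simple: the sampling SD of d is about 0.14-0.31 for true d of 0.2-0.8, and the small and medium bands are each 0.3 wide.

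Two milder measures for the same setting: for one given pair of arms, labels differ in 45-71% of trials at d of 0.2-0.8. At d = 0.5, labels two or more bands apart occur in 48%, 26% and 14% of trials (r = 0.5, 0.8, 0.9).

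**Does the ANOVA protect the labels?** With equal true gains the interaction is falsely significant in about 5% of trials, as it should be. Among trials with a non-significant interaction, labels still differ in 75-90% at true d of 0.2, 0.5 or 0.8.

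**Effect of the unnamed SD.** With equal pre and post SDs, d on the SD of change = d on the baseline SD / √(2(1 − r)).

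- r = 0.8: factor 1/√0.4 = 1.58, so a gain of 0.3 becomes 0.47
- r = 0.9: factor 1/√0.2 = 2.24, so 0.3 becomes 0.67 and 0.5 becomes 1.12

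The same data can therefore be medium on one SD and large on the other.

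**What a pairwise interval would show.** In baseline SD units, the standard error of a difference in change is √(2(1 − r)) × √(2/14). With 39 df the 95% half-widths are:

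- r = 0.5: SE 0.378, half-width 0.77 (0.95 with Bonferroni for three pairs)
- r = 0.8: SE 0.239, half-width 0.48 (0.60)
- r = 0.9: SE 0.169, half-width 0.34 (0.42)

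**The case against.** The strongest reply is that Section 3.5 already gives the between-programme question to the interaction test, which holds its 5% error rate, and pairs it with partial eta-squared. Within-arm d is then an ordinary descriptive measure for H1 and H2. All of that stands. It does not supply a pairwise estimate, which is what H3 and H4 need.

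A reader might go further and infer that the plan will judge programmes by their labels, or that equal gains would usually be reported as different. The documents support neither. Section 3.5 does not say that labels will be compared across arms, so that is a possible misreading and not a stated rule. Whether labels usually differ depends on the true gain, which the documents do not give. At large gains all arms tend to be labelled large. Even the conversion example shows this: at a gain of 0.5 baseline SD and r = 0.9, with d on the SD of change, labels differ in only 36% of trials.

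It is also fair to say that dividing by one common SD hardly helps by itself. At a gain of 0.3 baseline SD, labels differ in 88%, 77% and 60% of trials with a common SD (r = 0.5, 0.8, 0.9), against 89%, 80% and 67% with each arm's own baseline SD. Most of the disagreement is sampling error in the mean change.

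**Conclusion.** The point holds as a gap in estimation and reporting. The plan has no pairwise between-arm difference in change and no confidence interval, although its third and fourth questions and H3 and H4 turn on such differences. The labelled d values cannot substitute. With 14 per arm and equal true gains, the three labels disagree in roughly 60-90% of trials for true d of about 0.2-0.8, about 35-56% at d = 1.0, and 25% or less at d = 1.2. These rates rest on normal data, equal gains in all arms and correlations of 0.5 to 0.9. The dependence of d on the chosen SD is algebra and needs only a value for r.

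This is not an error in the main test, and the data to be collected are unaffected. It should still be changed, because the trial as planned could finish without an estimate that addresses H3 or H4.

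**What to change.** In Section 3.5:

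- For every outcome, and whatever the interaction p-value, report each of the three pairwise between-arm differences in change with a 95% CI in raw units. Optionally, also divide each by one SD, the pre-test SD pooled over all randomised players.
- State that conclusions on H3 and H4 rest on these differences and intervals.
- For H1 and H2, report the mean change in each arm with a 95% CI.
- If a within-arm d is kept, use the same pooled pre-test SD, call it descriptive and drop the verbal labels. Dropping the labels and adding the pairwise intervals matter more than the choice of SD.

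The cost is one paragraph in the plan and slightly more reporting, with no new data. Effects will look less clear-cut, because half-widths of 0.34 to 0.77 baseline SD (before any multiplicity adjustment) show how little 14 per arm can resolve. The ANOVA and its error rate stay as they are.
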